## **Objectives**

Transcranial Magnetic Stimulation (TMS) is an increasingly accepted neurostimulation- based treatment for major depressive disorder. While there is a growing anecdotal database supporting its use in bipolar depression we propose to collect open label efficacy and safety data in a small population of patients with clinically verified bipolar disorder.

## Aims and Hypotheses

The primary aims of this study are:

1. To provide clear open-label evidence that a standard course of TMS therapy can be effective for patients who have a diagnosis of bipolar depression and are currently on mood stabilizing medication.
2. To investigate the safety of TMS in a population at risk for activation from neuromodulation. In particular to observe if these patients are at risk for changing from a depressive state to a mixed or manic state.

Specific Hypotheses are that:

1. TMS will provide effective antidepressant treatment in patients with bipolar depression both type I and II.
2. TMS will show a shorter time to response in bipolar depressed patients compared with the available data in unipolar depressed patients.
3. TMS can be safely given in bipolar depression without inducing a manic or mixed episode switch in patients who are receiving adequate concurrent mood stabilizing medication.

## **Background**

The current FDA approved evidence base for the treatment of bipolar depression is limited to three atypical antipsychotics, one of which is paired with an SSRI. (Nierenberg et. al. 2015). The data analyzed from the STEP-BD study supports the notion that the use of antidepressants added to mood stabilizers provides no improved outcome but may carry the risk of precipitating or supporting a mixed or manic episode. (Sachs et. al., 2007, El-Mallakh et. al. 2015) A problem in developing safe and effective treatment paradigms for bipolar depression is that the population is so heterogeneous and subgroups may require different pharmacological interventions (Altshuler et. al. 2003, Goldberg et. al. 2015)

Transcranial magnetic stimulation has had a growing impact on the treatment of major depressive disorder. There is increasing use of this modality as insurers have increasingly provided support. Sheppard Pratt has been a leader in the adoption of TMS and our clinical TMS program using the Neuronetics NeuroStar

TMS Therapy® System (See Appendix 1) has treated over 200 patients over the past six years. While there is a clear evidence base for the use of TMS in MDD, there is as yet only a small anecdotal base for its use in bipolar depression (Connolly 2012, Nola 2013, Woźniak-Kwaśniewska 2015).

We are currently doing a retrospective look at our experience in treating bipolar depression with TMS which has represented about 15% of our patient base. ([name] data in review) A preliminary evaluation of our database shows that we have treated 45 patients with bipolar depression (See Appendix 2). Four patients had their course stopped by their clinician due to side effects; none of them met the criteria for mania or mixed state. Five patients had their course completed by a different TMS provider (closer to their home) and two had incomplete data. For the 34 patients who completed a course of treatment, 26 (76.5%) met response criteria by Montgomery-Asberg Depression Rating Score (MADRS) score and 12 met remission criteria (35%). These results are numerically superior to our experience in unipolar depression where our response rate is 62% and our remission rate is 31%. In general the treatment has been well tolerated and effective. Most of these patients have a long history of either poor efficacy or safety in the use of antidepressants and inadequate antidepressant response to the use of mood stabilizers or atypical antipsychotics.

A unique aspect of TMS for the bipolar depression patient is the ability to use the neurostimulation during the depressive episode without providing it as a chronic intervention as is the case with medication. The existing database is scant. While several trials are listed at [clinicaltrials.gov](http://clinicaltrials.gov), most of these data have remained unpublished. There is a current multi-center study, that uses the Brainsway H-Coil Deep TMS system, but the trial is still enrolling and likely years away from publication.

Given that Sheppard Pratt has an active, research based, clinical program, we would like to collect data prospectively and formalize diagnostic criteria, outcome measures and adverse events for this under-studied population. We will also be collaborating with the Mayo Clinic Rochester site.

### **Study Overview and Hypotheses**

We propose to screen patients with bipolar depression I or II, who are already on acceptable mood stabilization. They may or may not be on antidepressants at the time of screening but subjects on antidepressants would be taken off them before completing the screening phase. Those patients who have a depression of at least moderate severity without significant symptoms of activation or mania will be started on a course of open label TMS treatment of up to 35 sessions. Safety and efficacy assessments will be done weekly. Patients will complete a course of treatment when they meet remission criteria (MADRS score < 10) or at the end of 30 treatments, whichever comes first. Patients who are still judged to be improving between treatment 25 and treatment 30 will be eligible to complete up to five additional treatments as the discretion of each site's principal investigator.

Patients who meet response criteria (MADRS score decreases by at least 50%) will complete the full course of 30 to 35 TMS sessions. Patients will be withdrawn for safety concerns, particularly the onset of activation suggestive of mania or a mixed state.

Patients who meet response or remission criteria will be followed monthly for up to six months to evaluate the durability of response. They will be on standard mood stabilizing medications and psychotherapy per their clinician's discretion.

The primary study hypotheses are:

1. TMS will provide effective antidepressant treatment in patients with bipolar depression both type I and II.
2. TMS will show a shorter time to response in bipolar depressed patients compared with the available data in unipolar depressed patients.
3. TMS can be safely given in bipolar depression without inducing a manic or mixed episode switch in patients who are receiving adequate concurrent mood stabilizing medication

The secondary hypothesis is:

1. The majority of treatment responders will show adequate durability of response with remitters showing better durability.

### **Study Design**

Prescreening - Prospective study patients will be prescreened to determine the possible presence of bipolar depression and their willingness to be in a treatment study. The PI will introduce the study to the patient and give the patient an IRB-approved informed consent to read. The patient will have the opportunity to ask any questions about the trial and if desired, may take the consent form home to discuss with family, their physician, or others. Those who pass prescreening and want be in the study will be scheduled for a screening visit.

The study will be divided into three phases, Screening, Treatment and Follow-up.

#### Phase I: Screening

At screening all prospective subjects will sign the informed consent. A copy of the signed informed consent will be given to each participant. At the time of admission to the study, the patient's current treatment provider, if any, will be consulted, with the patient's permission, about the patient's participation in the study. After informed consent is obtained, patients will be eligible to be screened for inclusion in the study.

Screening will consist of several activities designed to validate that patients are suffering from bipolar illness, are currently in the depressed phase, and have been depressed in the current episode for at least four weeks but not longer than three years. The main screening tool will be the Mini International Neuropsychiatric Interview (M.I.N.I.) (Sheehan 1998). The Montgomery-Asberg Depression Scale (MADRS), the Young Mania Rating Scale (YMRS) and the Clinical Global Impression of Severity of Illness (CGI-S) rating will be done to confirm the patients' depression level and the absence of mania. As well, patients will be evaluated for the presence of any medical or psychiatric conditions that would either make it unsafe for them to participate in the trial (i.e., an unstable medical condition) or confound evaluation of the course of their bipolar condition (i.e., the presence of psychosis, substance abuse, or an eating disorder). Please see inclusion and exclusion criteria for specific qualifying parameters. When all inclusion criteria have been met and none of the exclusion criteria are present, patients are eligible to enter Phase II. They will be kept on mood stabilizing agents but will be tapered off of antidepressants. . As part of this initial evaluation, the study physician will evaluate the course of each subject's illness to determine the optimal medications to use during the course of TMS. If the subject, the referring physician or the study physician feels that it would be unsafe or unwanted to stop the antidepressant medication, the subject will be dropped from study participation and returned to routine clinical care. The course of TMS treatment will not start until two weeks after the antidepressant has been completed. This phase will last 1 to 28 days in order to accommodate possible changes in medication.

The subject's referring clinician will be advised of their patient's participation and asked not to change medications during the open label TMS treatment. The referring clinician will be invited to follow along or transfer care to the study physician until the subject completes or discontinues open label treatment, at which point care will return to the referring clinician who will be provided with a transfer note by the study staff.

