### Phase II: Open Label TMS Treatment

Once study patients are on stable medication and it is confirmed that they meet the entry criteria for Phase II they will begin a standard course of five times a week TMS treatment for six weeks. They will be assessed at each treatment visit for side effects, concomitant medication use, and once per week for severity of depression and evidence of any symptoms suggestive of mania or agitation. Any suggestion of mania or activation will be assessed by the study physician who will evaluate to determine if the subject can remain in the study or needs other intervention to manage emerging symptoms.

The MADRS, the 17-item Hamilton Depression Rating Scale (HAM-D17), the Quick Inventory of Depressive Symptomatology (Self-Report) (QIDS-SR16), the

YMRS, the C-SSRS (Columbia Suicide Severity Rating Scale) and CGI-S will be performed once per week. The CGI-Improvement Scale (CGI-I) will be done weekly starting at Visit 3. Treatment will continue until remission criteria is reached (MADRS score <10) or 30 treatments have occurred, whichever comes first. If improvement is continuing between treatment 25 and 30, treatments may be extended up to 35. Patients who are discontinued due to onset of manic or mixed symptoms will be followed until resolution of these symptoms. Patients who meet response criteria (MADRS score drops by at least 50%) or remission criteria will be followed in Phase III.

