### **Study Population**

It is estimated that up to approximately 30 patients will participate in the study at the Sheppard Pratt site with 20 additional patients enrolling at the Mayo Clinic Rochester site. Patients must have Bipolar I or Bipolar II depression as defined by the Diagnostic and Statistical Manual of Mental Disorders (DSM-5 criteria) and be taking a mood stabilizer acceptable to the principal investigator. They will not be allowed to take antidepressant medication. Their depression must be at least moderate in severity without significant symptoms of activation or mania.

Patients treated may come from the Retreat assisted living, outpatient services, outpatient practices of local psychiatrists, the Sheppard Pratt day hospital, or inpatient units. Patients enrolled at Mayo Clinic will come from their Mood program, Mood Clinic, Inpatient practice and the community. It is unlikely that current inpatients will qualify for this study as most of them will have co-morbidities, psychotic symptoms or mixed presentations which would exclude them.

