### Concomitant Therapy

In general, concomitant medications with primarily central nervous system activity will be kept to a minimum outside of the required mood stabilizing agent. All concomitant medications taken during the study will be recorded on the case report forms. Patients will be instructed to contact the investigator or study coordinator before taking any new prescribed medications, over-the-counter medications or supplements.

Subjects will be allowed to take up to 10 mg of Ambien per night for sleep.

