### **Statistical Methods**

- Sample Size

We are looking to collect sufficient data to demonstrate the efficacy and safety of TMS in bipolar depression. As this is an open label trial we will aim to treat 30 patients to achieve a reasonable sample size.

- Primary Efficacy Analysis

The primary outcome measure will be the percentage of patients who respond or remit after 30 to 35 treatments. We will subdivide patients based on the diagnosis of either bipolar I or bipolar II to compare effectiveness between those groups.

The other primary outcome will be the percentage of patients who meet criteria for onset of manic symptoms based on the YMRS. The patients will also be separated based on their diagnostic category.

- Secondary Efficacy Analysis

We will also look at the HAM-D and CGI to see the percentage of patients meeting response criteria.

For the patients meeting remission criteria, we will calculate the number of treatments required to achieve remission. Patients who only meet response criteria will be treated for 30 to 35 sessions.

Responders and remitters will also be followed for six months after the final treatment to see the durability of response. Percentage of patients' meeting relapse criteria will be calculated.

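### Response is coded on MADRS alone, so a patient who improves after a mid-course psychotropic start or increase counts as a TMS responder

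*Combined protocol and SAP*

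**What the plan says.** **Control of medication during TMS.** Under Phase I: Screening, the referring clinician is "asked not to change medications during the open label TMS treatment". Handing over care is optional: "The referring clinician will be invited to follow along or transfer care to the study physician". Concomitant Therapy says that, in general, "concomitant medications with primarily central nervous system activity will be kept to a minimum", apart from the required mood stabilizer. It tells patients to contact the study team before taking anything new, and has all medications recorded on the case report form. Study Population bars antidepressants. Phase II requires stable medication at entry and monitoring thereafter: "They will be assessed at each treatment visit for side effects, concomitant medication use".

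**Consequence of a change.** None is stated. Patient Withdrawal does not list a medication change, although it has a general clause covering the patient's well-being.

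**Outcome.** Study Overview and Phase II define response as a MADRS fall of at least 50% and remission as a MADRS score below 10. Statistical Methods then says: "The primary outcome measure will be the percentage of patients who respond or remit after 30 to 35 treatments". It gives no rule for patients whose psychotropic medication changed and no sensitivity analysis for them.

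**The concern.** The first aim is open-label evidence that a standard TMS course can be effective in patients on mood stabilizers. With one arm, the response percentage can be credited to TMS only if other active treatment stays constant between the first session and the rating. The plan protects this before treatment, through the antidepressant taper, the two-week wait and stable medication at entry. After the first session, the protection is a request, a contact-first instruction and record keeping.

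A patient who is not improving, has an antipsychotic or mood stabilizer started or raised, and then reaches a 50% fall is recorded as a TMS success. It is plausible, though not documented, that slow improvers are the patients most likely to be changed. If so, the error runs toward efficacy.

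**Working it through.** **Coding path.** Take a patient whose antipsychotic is started in the middle of the course and whose MADRS has fallen by half at the primary rating.

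1. Is the change prevented? Not by rule. The clinician was asked not to make it, and the antidepressant bar does not cover antipsychotics or mood stabilizers.
2. Does the change remove the patient? It is not a listed withdrawal reason, so removal is left to discretion.
3. Is it known? Yes, through the visit checks and the case report form.
4. Does it alter the coding? No. Both definitions use MADRS only.

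The patient is therefore a responder. No sentence says this outright. It follows from the definitions and the absence of any other rule.

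**Inputs for size.**
- n = 30 (Statistical Methods), or 30 + 20 = 50 (Study Population, two sites).
- Earlier clinic response, 26 of 34 (Background), used only as an illustrative level.
- Number of affected responders, k: not in the documents. I assume 1 to 5.

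**Plan's own figures.** 26/34 = 76.5%, which agrees with Background. The sample size of 30 has no formula behind it, so there is nothing to reproduce.

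**Weight of one patient.** 100/30 = 3.3 points; 100/50 = 2.0 points. Three patients: 10.0 or 6.0 points.

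**Effect of recoding k responders as non-responders.** Starting counts are 0.765 × 30 ≈ 23 and 0.765 × 50 ≈ 38. Rate = (start − k)/n, with exact Clopper-Pearson 95% intervals.

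| k | n = 30 | n = 50 |
|---|---|---|
| 0 | 76.7% (57.7–90.1) | 76.0% (61.8–86.9) |
| 1 | 73.3% (54.1–87.7) | 74.0% (59.7–85.4) |
| 2 | 70.0% (50.6–85.3) | 72.0% (57.5–83.8) |
| 3 | 66.7% (47.2–82.7) | 70.0% (55.4–82.1) |
| 5 | 60.0% (40.6–77.3) | 66.0% (51.2–78.8) |

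The drop equals the bias only if every recoded patient would otherwise have failed to respond. Where some would have responded anyway, the drop overstates it.

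**Expected bias under assumed rates.** Let p be the true response to TMS, q the share of would-be non-responders who get a change, and r the share of those who then respond. The observed rate is p + (1 − p)qr. With p = 0.50:
- q = 0.05, r = 0.3: 0.50 + 0.50 × 0.015 = 50.75%
- q = 0.10, r = 0.5: 0.50 + 0.50 × 0.05 = 52.5%
- q = 0.20, r = 0.5: 0.50 + 0.50 × 0.10 = 55.0%

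The shift is 0.75 to 5.0 points over this range, which at n = 30 is about 0.2 to 1.5 patients. All three inputs are assumptions.

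**The case against.** The strongest reply is that medication is far from uncontrolled. Antidepressants are barred, the study physician settles the medication for the course beforehand, entry requires stability, and changes are looked for at each treatment visit. These controls stand and should make changes less frequent. They do not say how a change is coded.

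Second, the rationale for mood stabilizers wants the study as naturalistic as possible, and counting outcomes whatever else was given is a legitimate choice. But the plan does not state that choice, and the resulting figure would describe TMS plus whatever was added, which is not what the first aim asks.

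Third, recoding can penalize a true TMS responder. The same rationale requires bipolar I patients to be within therapeutic range, so some dose adjustments have nothing to do with depression. This stands and is why the fix contains an exemption and a companion figure.

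Fourth, at n = 30 a shift of 3 to 10 points lies inside the sampling interval. That is true, but this bias has a likely direction and a larger sample would not remove it.

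Some stronger readings are tempting and are not supported:

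- A reader might infer that Phase II expects added treatment in patients who stay, from the words "needs other intervention to manage emerging symptoms". The sentence most plainly sets this as the alternative to remaining in the study, and it concerns activation or mania, not poor antidepressant response.
- A reader might infer that an antipsychotic is the expected intervention, because Background calls the approved evidence base "limited to three atypical antipsychotics, one of which is paired with an SSRI". That supports the view that such drugs can act on bipolar depression. It does not say they would be used during TMS.
- A reader might infer that patients receive TMS amid intensive care, from "the Sheppard Pratt day hospital, or inpatient units". That passage lists where patients may come from, and Study Population adds that current inpatients are unlikely to qualify.
- A reader might set 10 points against the Background gap of 76.5 − 62 = 14.5 points. Those are the clinic's own earlier rates, and Statistical Methods plans no test of response against 62%.

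**Conclusion.** The point holds as a gap in outcome coding. For patients with a mid-course psychotropic start or increase, the plan's definitions give responder status on MADRS alone, and the single-arm design cannot separate the added treatment from TMS. Each affected patient who would otherwise not have responded inflates the primary percentage by 3.3 points at n = 30 or 2.0 at n = 50.

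The total effect cannot be stated because the documents give no frequency, and it may be zero if the request is honoured. The upward direction rests on the plausible but undocumented assumption that changes go mainly to patients doing poorly. The study remains worth doing. Because it is open label, the rule should be fixed before results are seen.

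**What to change.** Add to the Primary Efficacy Analysis in Statistical Methods:

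- A patient who starts or increases an antidepressant, antipsychotic or mood stabilizer for depressive symptoms between the first TMS session and the primary rating counts as a non-responder in the primary percentage.
- A dose adjustment made only to keep a mood stabilizer in its therapeutic range is not such a change.
- The MADRS-only percentage is reported as a sensitivity analysis, with the number of patients affected.

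This is a coding rule. It does not say which medications should be allowed during TMS.

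**Cost.** One analysis rule, using medication data already collected. Applying it needs the reason for each change. The documents do not say that this is captured, so one case report form item, completed when the change is made, may be needed. The headline percentage may fall slightly, and some true TMS responders may be coded as failures; the gap between the two percentages shows the most that this could amount to.

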### Phase II: Open Label TMS Treatment

Once study patients are on stable medication and it is confirmed that they meet the entry criteria for Phase II they will begin a standard course of five times a week TMS treatment for six weeks. They will be assessed at each treatment visit for side effects, concomitant medication use, and once per week for severity of depression and evidence of any symptoms suggestive of mania or agitation. Any suggestion of mania or activation will be assessed by the study physician who will evaluate to determine if the subject can remain in the study or needs other intervention to manage emerging symptoms.

The MADRS, the 17-item Hamilton Depression Rating Scale (HAM-D17), the Quick Inventory of Depressive Symptomatology (Self-Report) (QIDS-SR16), the

YMRS, the C-SSRS (Columbia Suicide Severity Rating Scale) and CGI-S will be performed once per week. The CGI-Improvement Scale (CGI-I) will be done weekly starting at Visit 3. Treatment will continue until remission criteria is reached (MADRS score <10) or 30 treatments have occurred, whichever comes first. If improvement is continuing between treatment 25 and 30, treatments may be extended up to 35. Patients who are discontinued due to onset of manic or mixed symptoms will be followed until resolution of these symptoms. Patients who meet response criteria (MADRS score drops by at least 50%) or remission criteria will be followed in Phase III.

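### The scheduled mania check and the YMRS are weekly although patients attend about five times a week, so a switch between ratings can be noticed late or left out of the YMRS-based safety outcome

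*Combined protocol and SAP*

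**What the plan says.** All references are to the combined protocol and SAP.

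- **Attendance.** Under Phase II: Open Label TMS Treatment, "they will begin a standard course of five times a week TMS treatment for six weeks".
- **Each session.** The same section says "They will be assessed at each treatment visit for side effects, concomitant medication use".
- **Each week.** The same sentence then puts the mania check on the slower schedule: "once per week for severity of depression and evidence of any symptoms suggestive of mania or agitation". The rating scales follow it: "YMRS, the C-SSRS (Columbia Suicide Severity Rating Scale) and CGI-S will be performed once per week". Study Overview and Hypotheses agrees: "Safety and efficacy assessments will be done weekly".
- **Response to signs.** Phase II adds "Any suggestion of mania or activation will be assessed by the study physician", with no restriction to the weekly visit. The overview says "Patients will be withdrawn for safety concerns, particularly the onset of activation suggestive of mania or a mixed state".
- **After withdrawal.** Patient Withdrawal places an early termination visit one week later and names a MADRS and a CGI for it, but no YMRS. Phase II says that patients discontinued for manic or mixed symptoms are followed until these resolve, but names no scale.
- **Outcome.** Statistical Methods says "The other primary outcome will be the percentage of patients who meet criteria for onset of manic symptoms based on the YMRS". Its text gives no YMRS cut-off and mentions no rating outside the weekly schedule.

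**The concern.** A switch into mania or a mixed state is the harm this trial is set up to look for. It is the second primary aim, the third hypothesis and one of the two primary outcomes. Yet its structured check runs once a week, while the patient is seen about five times a week and is already asked about side effects each time.

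Two things are at stake. The first is timing: if activation is not volunteered as a side effect, sessions may continue until the next weekly check. The second is the outcome itself. The percentage is based on the YMRS, so a switch counts only if a YMRS is done while it is visible. A patient withdrawn mid-week for suspected mania may never reach the next weekly YMRS, and the termination visit does not list one. A case lost this way can only lower the switch percentage, and few cases are expected. Background reports 45 bipolar patients treated earlier at the lead site. Four had their course stopped for side effects, and none of those four met criteria for mania or a mixed state.

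**Working it through.** **Inputs from the plan.** Five sessions a week for six weeks, which gives 5 × 6 = 30 and reproduces the stated 30-treatment course. Scheduled mania check and YMRS: once a week. Treated patients: 30 (Statistical Methods), or 30 + 20 = 50 (the two sites in Study Population).

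**Not in the text, so assumed.** The weekday of the rating, whether it comes before or after that day's session, the YMRS look-back, the length of an episode, and onset spread evenly over the week.

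**Step 1: sessions between onset and the next scheduled check, if nothing else detects the switch.** Sessions run Monday to Friday.

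- Fixed weekday, check before the session, onset after that day's session. With a Monday check, Tuesday to Friday remain: 4 sessions.
- Fixed weekday, with onset between the check and that day's session, or with the check after the session: 5 sessions.
- Weekday varies, Monday one week and Friday the next, same order in both weeks. Check before the session: 5 + 4 = 9. Check after the session: 4 + 5 = 9.

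These are worst cases. With a fixed weekday and even onset, the mean runs from 1.5 sessions (Monday, check first) to 3.5 (Friday, check last).

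**Step 2: chance that a short episode falls wholly between weekly ratings.** For an episode of L days and a look-back of w days, P(missed) = max(0, 1 − (L + w)/7). With L = 4:

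- w = 0: 1 − 4/7 = 43%
- w = 2: 1 − 6/7 = 14%
- w = 3 or more: 1 − 7/7 = 0%

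Other lengths with no look-back: 86% for 1 day, 57% for 3 days, 29% for 5 days, 0% for 7 days. With a 7-day look-back, no episode of any length is missed.

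**Step 3: the withdrawal route.** This needs no assumption about look-back or episode length. If a patient is withdrawn between ratings, the next weekly YMRS falls away, the termination visit lists only the MADRS and CGI, and follow-up to resolution names no scale. On the text as written, a switch that was noticed and acted on need not produce a YMRS score.

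**Step 4: effect on the outcome.** One missed case is 1/30 = 3.3 points, or 1/50 = 2.0 points. At n = 30, the exact two-sided 95% upper limit for 0 cases is 1 − 0.025^(1/30) = 11.6%. For 1 case it solves (1 − p)^30 + 30p(1 − p)^29 = 0.025, giving 17.2%.

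**Step 5: what a per-session question could reach.** Treatment Compliance aims for no more than 3 consecutive days without treatment, so a 4-day episode during a compliant course includes at least one session. This shows that there is an opportunity to ask. It does not show that the question would detect every case.

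**The case against.** The strongest reply is that the plan does not confine detection to the weekly visit. Side effects are assessed at every session, and activation could well be reported there. Any suggestion of mania goes to the study physician whenever it arises. Adverse Events has site staff noting new events throughout, and Patient Withdrawal lists onset of manic or mixed symptoms as a reason to discontinue. A reader might infer that mania is looked for only once a week, or that TMS will carry on for four sessions after a switch. The documents support neither. Only the scheduled, structured check is weekly; continued treatment is possible but does not follow from the schedule; and four is neither stated nor an upper limit.

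Four further objections stand in part.

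- The missed-episode percentages depend on a look-back that the text does not give. Appendix 5 is listed by title only in the text supplied.
- Late detection concerns a switch that persists, while a missed short episode concerns one that resolves. The plan gives no frequency for either, so 3.3 points is the size of one case, not an expected bias.
- Dating onset only to the week harms no planned analysis, because the outcome is a percentage and no time-to-switch analysis is planned.
- Table 1, the schedule of events, is not in the supplied text and might list a per-session item.

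None of these answers the outcome problem. Physician review and adverse event recording do not produce a YMRS score, and the outcome is defined on the YMRS.

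**Conclusion.** The point holds in a limited form. The structured mania check and the YMRS are weekly, the per-session list omits activation, and the text provides for no YMRS when a switch is suspected or leads to withdrawal. A switch can therefore be noticed late, or be noticed and still be missing from the primary safety percentage. Any such omission lowers the percentage, by 3.3 points per case at n = 30 or 2.0 at n = 50. How many cases would be lost cannot be derived from the documents.

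The session counts (4, 5 or up to 9) assume that nothing else detects the switch. The 43%, 14% and 0% figures assume a 4-day episode and a stated look-back. A reader might conclude that the switch percentage is certainly biased; the documents show only that it can be, and in which direction. The weekly schedule is stated consistently and is not an internal contradiction. This is an inexpensive improvement to how a primary outcome is captured.

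**What to change.** 1. In Phase II: Open Label TMS Treatment, add a brief set question on manic or activation symptoms to the existing per-session side-effect check.
2. Keep the YMRS weekly. Also complete it on any day the question is positive or a switch is suspected, and at withdrawal for suspected manic or mixed symptoms. Say so in Patient Withdrawal as well.
3. In Statistical Methods, state that these unscheduled ratings count in the switch percentage under the same YMRS criteria as the weekly ones. The text gives no cut-off, so the criteria must be written down for this to work.
4. Record the date and session number of first signs descriptively, not as a new outcome.
5. Make Table 1 agree.

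These changes affect assessment and recording only. Clinical action stays with the protocol's own rules.

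The cost is about a minute at visits that already take place, one more line on the session form, occasional extra YMRS ratings and a few false-positive physician checks. No visits or staff are added. A set question will not be perfectly sensitive, so it reduces missed cases rather than removing them.
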